## 2.2 Outcome Measures

Primary Question: Does single event multi level chemoneurolysis (SEMLC) have an effect on energy expenditure and walking efficiency as measured by oxygen consumption (VO2) and gait parameters during the 6 minute walk test in 15 children diagnosed with cerebral palsy (CP)?

Hypothesis: If 15 children receive SEMLC, then energy expenditure (VO2) will decrease due to increased walking efficiency and gait parameters during the 6 minute walk test.

Secondary Question: Does SEMLC have an effect on 6 minute walking distance in 15 children diagnosed with CP?

Hypothesis: SEMLC will increase the distance walked during the 6 minute walk test.

Secondary Question: Does SEMLC have an effect on the Gross Motor Functional Classification System (GMFCS) classification in 15 children diagnosed with CP?

Hypothesis: SEMLC will decrease a child's GMFCS classification due to increased physical function.

Secondary Question: Does SEMLC have an effect on ankle muscle spasticity as measured by the Modified Ashworth Scale (MAS) and the modified Tardieu Scale?

Hypothesis: SEMLC will decrease ankle muscle spasticity and in turn improve MAS and modified Tardieu Scale scores.

Secondary Question: Does SEMLC have an effect on dynamic balance during walking in 15 children diagnosed with CP?

Hypothesis: SEMLC will increase dynamic balance during walking.

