## 1. INTRODUCTION

Cerebral palsy (CP) is a movement and postural disorder due to lesion to immature brain. Spasticity is the most common movement disorder in children with cerebral palsy (CDC) and causes difficulty with walking, musculoskeletal complications such as hip dislocation, scoliosis and joint contracture, pain and balance issues (Balaban et al., 2012). Spastic muscles are stiff and weak (Campbell & Ball, 1978). A combination of spasticity and weakness in children with CP makes them walk difficult and less efficient. Spasticity management has been very important for children with CP for activity of daily living including walking (Massin & Allington, n.d.) Using botulinum toxin A (BoNT-A) injections to control spastic lower limbs became almost first line treatment for children with CP to improve gait, range of motion and quality of life. (Ade-Hall & Moore, 2000). Several studies reported that children with CP showed higher energy expenditure during walking compared to typically developing peers. (Balaban 2007 & Rose et al 1990 Steele K et al 2017) This increase is due to combination of the mechanical inefficiencies during ambulation caused by spasticity (Reddihough et al., 2002), muscle co-contraction ((Balaban et al., 2012), limited range of motion, muscle weakness and loss of balance (Norman, 2004). Perhaps, improving coordination of walking by reducing in spasticity with BoNT-A may improve energy expenditure by improving coordination of muscle activity which is related to peak power output (Wakeling et al, 2010). Energy expenditure is an objective measure of evaluating the energy cost required for movement (Rose et al., n.d.) Generally, the oxygen consumption (VO2) is used to measure energy expenditure and one of the most significant markers of aerobic fitness and endurance (*ACSM's Advanced Exercise Physiology*, 2006). The rate of oxygen consumption (mL/kg/min) was significantly higher in the children with diplegia than in those with hemiplegia or with spina bifida or the healthy children (Rose et al., n.d.). Oxygen cost (mL/kg/m) was significantly higher, and velocity was significantly slower in all the groups with disability than in the healthy children (Duffy and Graham 2014). Balaban et al showed that botulinum toxin A injections to spastic gastric muscles decreased VO2 and gait parameters at 2-month post injections. We hypothesized that BoNT-A injections to spastic lower limbs of ambulant spastic CP decrease energy expenditure during walking. The aim of this study is to investigate the effect of spasticity management using Dysport® (AbobotulinumtoxinA) on the walking efficiency, oxygen consumption and gross motor function and gait parameters of children with CP.

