
## 2. DESIGN

This study is a single center, open label study.

We seek to recruit 15 children diagnosed with Cerebral Palsy (CP) in order to determine the efficacy of single event multi level chemoneurolysis (SEMLC) with Dysport® on energy expenditure as measured by oxygen consumption (VO2) during the 6 minute walk test.

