The CP QOL for children, adolescents, and caregivers will be used to assess quality of life and wellbeing across multiple domains of life (4). For children 4-12 years, we will give the primary caregiver version to their parent or guardian. For children 9-12 years, we will give the child self-report version. For adolescents 13-18 years, we will give the teen self-report version as well as the primary caregiver version to their parents or guardian. The sum for each domain will be calculated as well as the total sum.

Gait analysis and the 6 Minute Walk Test (6MWT) with oxygen consumption measurement (energy expenditure) will be performed in the Department of Rehab by an exercise physiologist. Children will be given at least a ten minute rest between measures.

Gait analysis will be measured with the GAITRite® mat, a commercially available instrumented mat for collection of gait data. The GAITRite system is an electronic walkway that connects to a computer, and automates the measurement of temporal (timing) and spatial (distance) gait parameters, such as cadence, step length and velocity. The standard GAITRite walkway is (5m long) and contains 13824 sensors encapsulated in a roll up mat to produce an active area 0.6 m wide and 4.25 m long. The walkway is portable, can be laid over any flat surface and requires no placement of any devices on the patient. GAITRite uses no radiation, electricity or ultrasound to measure these parameters and is therefore a safe method for evaluating walking function, even during pregnancy. The system has been validated for use in healthy children and children with movement disorders (such as cerebral palsy, and spinal muscular atrophy) (5, 6). The laboratory consists of a 10-meter walkway. The GAITRite mat is placed in the middle of the 10 meter walkway to collect data on steady state gait without the influence of gait initiation and termination. Subjects will be asked to wear the same shoes and orthoses throughout the study. A gait aid can be used during the test if the child cannot walk without it. Subjects will be asked to begin walking at a starting position located 1.5 meters from the mat and walk at their preferred typical speed until a termination position marked on the floor (1.5m from the end of the mat). Each subject will perform five trials of walking at their preferred speed. We will compute gait

velocity, step length, cadence, percent time spent in double support, foot angle, and base of support.

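### Primary VO2 comes from a self-paced walk and is not related to its speed or distance, so it can rise despite better efficiency and fall through slowing alone; prespecify oxygen cost per metre

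*Combined protocol and SAP*

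**What the plan says.** The primary question in section 2.2 concerns an effect on "energy expenditure and walking efficiency as measured by oxygen consumption (VO2) and gait parameters during the 6 minute walk test". The hypothesis is that "energy expenditure (VO2) will decrease due to increased walking efficiency and gait parameters during the 6 minute walk test". No unit is given for VO2. A secondary hypothesis about the same test is that "SEMLC will increase the distance walked during the 6 minute walk test". Section 2 states the objective as the effect "on energy expenditure as measured by oxygen consumption" in that test and does not mention efficiency.

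The Introduction treats efficiency and consumption as different things. The stated aim is the effect "on the walking efficiency, oxygen consumption and gross motor function and gait parameters of children with CP". The background separates a rate, "The rate of oxygen consumption (mL/kg/min) was significantly higher in the children with diplegia", from a cost, "Oxygen cost (mL/kg/m) was significantly higher, and velocity was significantly slower in all the groups with disability".

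Under section 2.3 the child chooses the pace of the six-minute walk and may stop early. VO2 is recorded during a three-minute rest and during the walk, and distance is recorded once, at six minutes. Gait velocity comes from a different test on the GAITRite mat ("Each subject will perform five trials of walking at their preferred speed"), with at least ten minutes of rest before the six-minute walk.

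No section divides VO2 by speed or distance, subtracts the resting value, or says how VO2 and distance are to be read together.

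**The concern.** Given the Introduction's wording, and with no cost calculation anywhere, VO2 in section 2.2 reads most naturally as the rate in mL/kg/min. That rate depends on how fast the child walks as well as on how economically. The primary hypothesis (VO2 down) and the distance hypothesis (distance up) therefore pull the same measurement in opposite directions.

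Two wrong conclusions become possible. If children walk further, as predicted, a real efficiency gain can show as unchanged or higher VO2. If they slow down, the lower VO2 can be attributed to better efficiency when there was none. The GAITRite velocity cannot settle the matter, because it is not the speed at which VO2 was recorded.

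The raw data needed for a cost per metre are collected either way. At stake is the prespecified primary conclusion: a cost measure adopted after the data are seen would be post hoc.

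**Working it through.** The plan gives no expected change, standard deviation or calculation for VO2, so there is no figure of its own to reproduce. The check has a part that needs no inputs and a part that rests on assumed ones.

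**1. Break-evens, no assumed inputs.** Let v be mean speed in the six-minute walk, so v is proportional to distance over the fixed six minutes. Let G = VO2 / v be gross cost per metre. Then VO2 = G × v.

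- Distance up by a fraction g: VO2 falls only if G falls by more than g/(1+g).
- Distance down by a fraction d: VO2 still falls unless G rises by 1/(1−d) − 1 or more.

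| Change in distance | VO2 falls only if gross cost |
|---|---|
| +5% | falls by more than 0.05/1.05 = 4.8% |
| +10% | falls by more than 0.10/1.10 = 9.1% |
| +20% | falls by more than 0.20/1.20 = 16.7% |
| −5% | rises by less than 1/0.95 − 1 = 5.3% |
| −10% | rises by less than 1/0.90 − 1 = 11.1% |
| −20% | rises by less than 1/0.80 − 1 = 25.0% |

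If resting VO2 is equal at both visits, VO2 − rest = N × v, where N is net cost, and the same thresholds apply to N.

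**2. Illustration, assumed inputs.** The model is VO2 = rest + C × v, so N = C and G = rest/v + C. Base values are rest 5 mL/kg/min, C 0.25 mL/kg/m and v 50 m/min, giving VO2 = 5 + 12.5 = 17.5 and G = 0.350. Ranges in brackets cover rest 4 to 7, C 0.15 to 0.40 and v 35 to 60.

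- Net cost 5% better, distance +10%: 5 + 0.2375 × 55 = 18.06, VO2 **+3.2%** (+1.9 to +3.9).
- Net cost unchanged, speed −10%: 5 + 0.25 × 45 = 16.25, VO2 **−7.1%** (−4.3 to −8.6).
- Net cost 5% worse, speed −10%: 5 + 0.2625 × 45 = 16.81, VO2 **−3.9%** (−2.4 to −4.7).

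In the second case, a true 10% net-cost gain at unchanged speed gives the same value, 5 + 0.225 × 50 = 16.25. The rate alone cannot tell the two apart.

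**3. Gross or net cost.**

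- Walking 10% faster with C unchanged gives G = 5/55 + 0.25 = 0.3409. Gross cost falls by 2.6% (1.3 to 5.2); net cost does not move.
- A real 5% net gain at the same speed gives G = 5/50 + 0.2375 = 0.3375, a fall of only 3.6% (2.1 to 4.3).
- A 10% error in resting VO2 moves net cost by 0.5/12.5 = 4.0% (1.7 to 13.3) and gross cost not at all.
- With an assumed 10% SD of that error at each visit, the change per child gains √2 × 4.0 = 5.7 percentage points of SD. The mean of 15 children gains 5.7/√15 = 1.5 points of standard error (0.6 to 4.9).
- Net cost is free of pace only if the linear model holds. If walking VO2 extrapolates to 1 or 2 mL/kg/min above rest at zero speed (assumed), walking 10% faster lowers net cost by 0.7% or 1.3% and gross cost by 2.9% or 3.3%.

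**4. Averaging window.** Assume an exponential rise in VO2 with a time constant of 30, 45 or 60 s. Averaging all six minutes understates net VO2 by 8.3%, 12.5% or 16.6%; averaging from minute 3 to minute 6 understates it by 0.04%, 0.4% or 1.6%. If a child stops at 3 minutes at one visit and completes the other at the same speed, whole-walk averages show a spurious net-cost change of −13.8% (−9.0 to −18.0). Comparing the same minutes removes it if the time constant is unchanged.

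**The case against.** The strongest reply is that section 2.2 gives no unit, so cost per metre may have been intended, and that VO2 rate is a legitimate measure of energy expenditure, which is all that section 2 claims. Both points narrow the criticism without removing it. It applies to the efficiency claim and to the causal wording of the hypothesis, not to VO2 as a measure of expenditure. If cost was intended, it is still not prespecified, and the same edit is needed.

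The two hypotheses can also both be true: distance can rise by 10% and VO2 still fall if cost falls by more than 9.1%. The documents give no expected changes, so the likelihood of masking or reversal cannot be stated. That stands. Only its possibility, and the thresholds for it, are shown.

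Net cost has weaknesses of its own. The three-minute rest also serves to accustom the child to the mask, so it may not be a settled baseline. The added standard error reaches 4.9 points at the top of the range, close to the 5% gain in the example. Drift matters in both directions. A resting reading 5% lower at follow-up raises net cost by 2.0% (0.8 to 6.7), against the hypothesis; one 5% higher lowers it by as much, in its favour. This is why the choice between net and gross is left to the team, provided it is made in advance.

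Finally, VO2, resting VO2 and total distance are recorded anyway, so a whole-walk cost can be computed later. The loss is of prespecification rather than data, but in a 15-child open-label study with no control group described, that loss matters.

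**Conclusion.** The concern holds, and the plan should be changed before analysis. As written, the primary measure can give the wrong sign for efficiency in the situation the protocol itself predicts, and can count slowing as a gain.

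The break-evens (4.8%, 9.1% and 16.7% for longer walks; 5.3%, 11.1% and 25.0% for shorter ones) follow from an identity and rest on no assumed values. Their extension to net cost needs equal resting VO2 at the two visits. The percentage changes in VO2 (+3.2%, −7.1%, −3.9%) rest on a linear model and assumed values for rest, cost and speed. Their signs hold across the whole range examined. The reading of VO2 as a rate is an inference from the Introduction, but the gap remains under either reading.

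**What to change.** In section 2.2:

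- Make oxygen cost per metre (mL/kg/m) in the six-minute walk the primary efficiency measure, word the efficiency hypothesis in those terms, and report VO2 rate (with its unit) and distance beside it.
- Report net cost, (walking VO2 − resting VO2) / walking speed, and gross cost, walking VO2 / walking speed. Name the primary one before any data are analysed. Net cost is suggested, because the pace effect in gross cost favours the hypothesis when children walk further and does not average out, whereas random error in the resting reading does. If the team finds the rest period too unstable and names gross cost, a gain should be claimed only when net cost agrees in direction.
- State the averaging window, for example minutes 3 to 6 with speed over the same minutes, and use the whole walk as a sensitivity analysis.
- For a child who pauses or stops early at one visit, compare the same uninterrupted minutes at each visit. For a stop before minute 3 these lie outside the main window, so repeat the analysis without such children.
- Say that the gait parameters come from the separate GAITRite test.

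In section 2.3, record weight at each six-minute-walk visit (the follow-up lists do not itemise it), distance at each minute, and the time and distance at any pause or stop.

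The choice of week 4 or week 12 as the primary visit is a separate matter, but it must also be fixed for the primary conclusion to be fully prespecified.

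The cost is wording and minor recording, with no new visit or device. The downsides are a noisier ratio for very short walks, the resting-reading noise that net cost carries, and some remaining pace effect if the linear model fails.

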### *Subject Visits:*

- **Baseline:** Consent, Modified Ashworth Scale, modified Tardieu Scale, CP Quality of Life Questionnaire for Children/Adolescents, 6 minute walk with VO2 and gait analysis
- **Treatment:** SEMLC treatment

- **4 week follow-up:** Modified Ashworth Scale, modified Tardieu Scale, CP Quality of Life Questionnaire for Children/Adolescents, 6 minute walk with VO2 and gait analysis
- **12 week follow-up:** Modified Ashworth Scale, modified Tardieu Scale, CP Quality of Life Questionnaire for Children/Adolescents, 6 minute walk with VO2 and gait analysis

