## 2.1 Participants

All subjects will be recruited from [name] Physical Medicine & Rehabilitation clinic. [name] will approach eligible patients and their parents in order to explain the study and to determine interest. A researcher of the study team will email and/or telephone call eligible participants on behalf of [name] and with her permission to inform the parents of the eligible participant of the study.

Inclusion Criteria:

- Age: 5-17 years. *Must be <18 prior to injection.*
- >10 kilograms at screening and injection visits
- Diagnosis of spastic diplegia OR mild- to moderate spastic quadriplegia Cerebral Palsy
- Gross Motor Function Classification System level: I, II, III
- Ability to ambulate independently without aid, equinus gait
- Absent of joint or bone deformities
- Eligible to receive SEMLC
- Cooperative and tolerant to testing procedures during clinic screening
- Presence of spasticity in one or both legs
- Be on a stable dose and regimen if on any prescribed medication/s
- Parent must have signed written informed consent and the Patient Authorization for Use and Release of Health and Research Study Information

Exclusion Criteria:

- Ankle contractures no more than -10 degrees with the knee extended
- Hemiplegia
- Wheelchair dependent
- Received Botulinum toxin within previous 4 months
- Uncontrolled epilepsy or certain types of seizures
- Fracture in the study limb within previous 12 months
- Infection or skin disorder at planned injection site
- Shortness of breath or other respiratory issues
- Uncontrolled clinically significant medical condition
- Received phenol or alcohol block in the study limb within previous 6 months
- Surgery in the study limb within previous 12 months
- Serial casting within previous 12 months
- New physiotherapy and/or orthotic regimen <1 month before study start. (physiotherapy and/or orthotic regimen will be permitted if it began >1 month before study start and maintained throughout study)

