## 2.3 Procedures

Baseline (within 1 week prior to Dysport® treatment):

Before initiating any study procedures the informed consent will be discussed and signed with the parent(s) of the participants and the researcher will answer any questions. If capable of providing assent (>7 years old), the participant will sign the assent form. Once the consent and assent forms are discussed and signed the following assessments will be performed: demographics, height, weight, calculated body mass index (BMI), Modified Ashworth Scale (MAS), modified Tardieu Scale, range of motion of major joints (i.e., hip, knee, ankle), the Cerebral Palsy Quality of Life Questionnaire (CP QOL) for Children (9-12 years) or Adolescents (13-18 years), and the CP QOL for caregivers, 6 minute walk test (with mobile oxygen consumption), and gait analysis.

Degree of spasticity/tone in the lower limbs will be measured by the Modified Ashworth scale while the participant is relaxed and in the supine position (1). If testing a muscle that primarily flexes the hip, knee, or ankle joint the investigator will place the joint in a maximally flexed position and move the joint to a position of maximal extension over one second. If testing a muscle that primarily extends the hip, knee, or ankle joint the investigator will place the

joint in a maximally extended position and move the joint to a position of maximal flexion over one second.

The Modified Tardieu Scale will be used to assess spasticity by measuring different angles of muscle reaction in response to a passive force (2). Two angles will be measured from each major joint (i.e., hip, knee, ankle): R1, the angle in which clonus was felt during a quick passive stretch of the muscle; R2, the angle of full passive range of motion. The difference between the two angles ( $R2 - R1$ ) will be recorded for each muscle group. The participant will be lying supine for all angle measurements.

Range of motion of the lower limbs (hip, knee, ankle) will be measured by passively moving the patient's joint to a point of resistance where then the joint angle will be measured by a goniometer. Hip flexion will be measured with the patient lying supine. Knee flexion and extension will be measured with the patient lying supine. Ankle dorsiflexion will be measured with the knee extended in the supine position. The Thomas Test will also be used to assess hip flexion with the patient lying in supine (3).

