After at least a ten minute rest, oxygen consumption via the breath-by-breath method using a portable spirometric device (Cosmed K5; COSMED USA Inc, Concord, CA) will be determined while the participant performs the 6MWT (7). After instruction the participant will don the face mask and a 12 lead ECG will be applied. In order for the child to become comfortable with the face mask, a three minute rest period will be given while resting heart rate (HR) and oxygen consumption (VO2) is measured. After the three minute rest, the participant will begin the 6MWT while the K5 mobile device collects gas exchange variables [VO2, VCO2, respiratory exchange ratio (RER)] and HR will be monitored via the 12-lead ECG as well as cardiac rhythm. Participants will be instructed to walk at their normal walking pace as far as they can for six minutes. They will be allowed to walk with any orthoses and/or assistive devices however the same orthoses and/or devices will be used throughout the study. The participant can stop at any time if they feel dizzy or fatigued to the point of increased risk of falling. The total distance walked (meters) will be recorded at six minutes.

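### Change in GMFCS level is a secondary question, but the plan specifies no GMFCS rating after treatment

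*Combined protocol and SAP*

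**What the plan says.** Section 2.2 (Outcome Measures) asks: "Does SEMLC have an effect on the Gross Motor Functional Classification System (GMFCS) classification in 15 children diagnosed with CP". The accompanying hypothesis is directional: treatment is expected to lower a child's "GMFCS classification due to increased physical function". The aim at the end of section 1 (Introduction) also names gross motor function.

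The only other mention of the scale is the inclusion criterion in section 2.1 (Participants): "Gross Motor Function Classification System level: I, II, III".

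The visit summary in section 2 (Subject Visits) gives the same measurements at baseline, 4 weeks and 12 weeks: "Modified Ashworth Scale, modified Tardieu Scale, CP Quality of Life Questionnaire for Children/Adolescents, 6 minute walk with VO 2 and gait analysis". Section 2.3 (Procedures) gives a fuller baseline list, which begins "demographics, height, weight, calculated body mass index (BMI), Modified Ashworth Scale (MAS), modified Tardieu Scale, range of motion of major joints" and goes on to quality of life, the 6-minute walk with oxygen consumption, and gait analysis. The 4-week and 12-week paragraphs say that the baseline procedures are repeated and list them again. None of these lists includes GMFCS.

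**The concern.** A hypothesis of decrease can be tested only if the level is rated before and after treatment, at a known time and by a known rater. The plan specifies no post-treatment rating. Its only pre-treatment level is the one implied by eligibility, with no date or rater.

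What is at stake is the secondary question itself, which would have no data to answer it. GMFCS is also the only outcome in section 2.2 that carries the gross motor function label used in the study's aim. If the gap were noticed late, a level might be assigned retrospectively or at an unplanned time. In an open-label, single-center study with a stated expected direction, such a rating would be hard to defend.

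**Working it through.** No calculation in the plan needs reproducing. The check compares what section 2.2 asks for with what the other sections say will be collected.

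**Step 1: every place where GMFCS could be scheduled or described.**

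| Place | Content | GMFCS rating? |
|---|---|---|
| 2.1 Participants | Eligibility, levels I to III | Entry level implied; no rater or date |
| 2, Subject Visits (baseline, 4 and 12 weeks) | Ashworth, Tardieu, quality of life, 6-minute walk with oxygen consumption, gait analysis | No |
| 2.3, baseline list | The above plus demographics, height, weight, BMI and range of motion | No |
| 2.3, measurement descriptions | Methods for Ashworth, Tardieu, range of motion, quality of life, gait, 6-minute walk | No |
| 2.3, injection/treatment | Drug, guidance, anesthesia, setting | No |
| 2.3, 4 weeks | Repeat of baseline, with list | No |
| 2.3, 12 weeks | Repeat of baseline, with list | No |

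**Step 2: could the repeat of baseline bring in a rating?** No. The baseline assessments contain no GMFCS rating, so repeating them does not produce one.

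**Step 3: could GMFCS be a measurement that the lists simply leave out?** The lists are not complete. Section 2.3 describes items that no list names, for example "The Thomas Test will also be used to assess hip flexion with the patient lying in supine", and, before the walk, "a three minute rest period will be given while resting heart rate (HR) and oxygen consumption". Each of these is described in the procedure text. GMFCS is in neither the lists nor the text.

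**Step 4: comparison with the other secondary questions.** Section 2.2 has four: walking distance, GMFCS level, ankle spasticity and dynamic balance.

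- Walking distance has a recording step: "The total distance walked (meters) will be recorded at six minutes".
- Ankle spasticity has described Ashworth and Tardieu methods.
- Dynamic balance has no named measure, but gait variables that could bear on it (double-support time, base of support) are collected at every assessment visit.
- GMFCS level has no specified follow-up data of any kind.

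The count is therefore 1 of 4.

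**Step 5: size of the remedy.** The planned number is 15 children.

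- Rating at baseline, 4 weeks and 12 weeks: 15 × 3 = 45 ratings.
- Rating at baseline and one follow-up visit: 15 × 2 = 30 ratings.
- If the eligibility level is formally recorded as the baseline value, only follow-up ratings are added: 15 × 2 = 30 for two visits, or 15 × 1 = 15 for one.

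**The case against.** The best defence has four parts.

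- **The lists are abbreviated.** The visit summary omits range of motion, height and weight, which section 2.3 includes, so the absence of GMFCS from the summary proves little. The Thomas Test and the resting measurements are also better seen as components of listed assessments than as unlisted ones. Both points are fair. They mean that the finding rests mainly on section 2.3, where the fuller baseline list, the measurement descriptions and both follow-up lists omit GMFCS.
- **An entry level must exist, and follow-up repeats baseline.** Eligibility does require a level. But it is not among the baseline assessments that follow-up repeats, so this supplies no post-treatment value.
- **The 1-of-4 count flatters the other questions.** Dynamic balance is not tied to any measure either. This stands as a caution: the count says only that GMFCS is the one question with no follow-up data, not that the other three are fully specified.
- **It is a small matter.** This is one secondary question in a 15-child open-label study. The primary question is untouched, and walking distance and gait velocity remain. That limits the importance of the gap without closing it: neither measure is a GMFCS level, and a missed follow-up rating cannot be fully recovered once the visit has passed.

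**Conclusion.** The concern holds. The plan states a directional hypothesis about change in GMFCS level and specifies no post-treatment rating, rater or time point. One of four secondary questions therefore cannot be answered from the data the plan says it will collect. The primary question on oxygen consumption is not affected. The plan should be corrected before follow-up visits take place, but the gap does not threaten the study as a whole.

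The conclusion assumes that the pages removed before review (title, signature, contact or consent pages) contain no assessment schedule. It does not depend on any assumption about effect size, variability or dropout.

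**What to change.** Choose one of two changes.

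1. **Add the measurement.** Put a GMFCS rating in the baseline assessments and in the 4-week and 12-week visits, in both the visit summary and section 2.3. Name who rates it (existing study staff, preferably the same rater for a given child throughout), and report change from baseline. State that children at level I on entry cannot show the hypothesised decrease, and report how many there are. The cost is at most 45 brief open-label ratings, fewer if only one follow-up visit is rated or the eligibility level is recorded as baseline. No visits are added.
2. **Delete the question.** Remove the GMFCS question and hypothesis from section 2.2 and keep GMFCS as a baseline descriptor. The cost is one fewer secondary claim. The aim in section 1 would then need rewording, because no outcome in section 2.2 would carry the gross motor function label.
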